4 RESEARCH QUESTION/AIM(S)

Primary aim:

Establish and validate a clinical protocol for microdialysis derived chemistry driven therapy in TBI and see if it improves lactate:pyruvate ratio (<25).

Secondary aims:

Determine the optimal strategies for correcting abnormalities in microdialysis derived parameters.

Determine the inflammatory, tissue and functional outcome for patients suffering from different defined pathological conditions

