3 THEORETICAL FRAMEWORK

We aim to include all traumatic brain injured patients admitted to the neuro-critical care unit that are being monitored and have multi-modality monitoring already in place. As all patients will follow the same protocol, we will minimize the risk of selection and researcher bias. As the patient will be unconscious during this process, next of kin will be asked for consent. As mentioned, this is a structured form of the standard treatments already provided in intensive care.

We will specifically identify patients in whom the microdialysis lactate:pyruvate ratio (LPR) increase above 25. This threshold has been proven to relate to a worse outcome after head injury. This will trigger our protocol which will consist of the following steps:

1. If ICP >20 mmHg, we will aim to escalate intracranial pressure decreasing measures by administering hypertonic saline (5%) 100 ml and if necessary continue on with further ICP decreasing measures.
2. If the brain oxygen pressure falls <15 mmHg, and the pressure reactivity index is >0.3 (an indication that the normal auto-regulation of the brain blood flow is not functioning properly), will increase the cerebral perfusion pressure by 10-20 mmHg.
3. If this still does not improve the brain oxygen pressure, we will increase the flow of inspired oxygen up to a maximum of 60-80%.
4. These steps do not adjust the LPR and if there is a decrease in glucose in the affected brain tissue (<1 mmol/l), we will increase the plasma glucose levels to a maximum 10 mmol/l in order to ensure that the correct amount of nutrients is being delivered, using 50% dextrose (sugar) solution.
5. If all the above steps fail to improve the LPR, it could be due to mitochondrial failure, the powerhouse of the cell. There are currently no approved therapies for this condition. However, at the treating physicians discretion, energy supplementation (e.g. succinate) or neuro-protective drugs (e.g. cyclosporine A) could be provided.

Directed management in brain injury.

Following a 6 month period, we will see the patients in our outpatient clinic to assess functional outcome. This is part of the patient's standard clinical care as all our patients are offered clinical follow up in this way.

We will collect any biological samples that are available as part of the standard clinical care of the patient and will not subject the patients to any additional procedures. This would consist of:

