4.1 Objectives

1. We wish to determine which of the provided therapies that was superior to others in improving the deranged brain metabolism.
2. We also wish to determine the inter-relationships between parameters detected using the microdialysis and other monitoring techniques, such as brain oxygen saturation and perfusion pressure in the damaged brain, and how microdialysis may complement these techniques.
3. How the protocol will alter cytokine, chemokine and markers of brain damage markers (S100B) in serum and microdialysate for patients suffering from different pathological states?
4. How will the functional outcome distribution be for patients suffering from different pathological states?

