7.2.1 Size of sample

The aim is to reach a sample size where there is a statistical difference between patients with different pathological targets. It is difficult to assess what this sample size is considering this has never been done before, but we estimate that a n=100 will suffice.

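### The primary aim promises to validate the treatment protocol, but one uncontrolled single-centre cohort of about 100 can only estimate the response; ranking strategies in the same patients is exploratory and confounded

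*Protocol*

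**What the plan says.** Protocol section 4, repeated in the Study Summary, gives the primary aim as "Establish and validate a clinical protocol for microdialysis derived chemistry driven therapy in TBI", together with seeing whether LPR improves to below 25. A secondary aim is to "Determine the optimal strategies for correcting abnormalities in microdialysis derived parameters". Objective 1 in section 4.1 reads "We wish to determine which of the provided therapies that was superior to others in improving the deranged brain metabolism". The outcome in section 4.2 is LPR below 25, broken down by treatment strategy.

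Section 3 sets out the algorithm in advance. When LPR exceeds 25, "This will trigger our protocol which will consist of the following steps", and five numbered steps follow. It adds "As all patients will follow the same protocol, we will minimize the risk of selection and researcher bias". Section 6 describes a prospective study at one centre. The analysis text in section 5 compares patients grouped by pathological target. Section 7.2.1 sizes the study so that a difference between those groups will show, and says "It is difficult to assess what this sample size is considering this has never been done before, but we estimate that a n=100 will suffice".

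The Study Summary labels the trial as controlled and non-randomised, but no control group is described anywhere in the text.

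**The concern.** Establishing a protocol and validating it are two tasks. Validation needs evidence beyond the patients in whom the protocol was first tried: an independent cohort, a held-out part of this one, another site, or at least a comparator. None is described. Additional patients or sites are matters of design and recruitment, so a protocol would not normally leave them to the statistical analysis plan.

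Objective 1 and the secondary aim raise a second issue. If several strategies are compared and the one with the highest observed success is reported as best, that figure is biased upwards on average, because chance helps to decide which strategy comes first.

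At stake is what the trial may conclude. As the aim is worded, a single-centre exploratory result could be published as a validated treatment protocol, with the raw success rate of the leading strategy beside it.

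**Working it through.** **1. The planned size.** The figure of 100 (sections 7.2.1 and Study Summary) cannot be reproduced. The protocol gives no significance level, power, effect, response rate or number of groups. Its stated basis is a difference between pathological targets, not validation.

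**2. What the cohort can deliver for the primary aim.** The five steps are listed before enrolment, so no strategy is chosen when the algorithm is judged as a whole. The selection bias in the overall proportion reaching LPR below 25 is therefore 0. Assuming one yes/no response from each of 100 patients, the 95% half-width is 1.96 × √(p(1−p)/100):

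- p = 30% or 70%: 1.96 × √(0.21/100) = 9.0 points
- p = 50%: 1.96 × √(0.25/100) = 9.8 points

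This is a usable estimate of response. It has no counterpart in other patients or under other care.

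**3. Whether the cohort could be split.** Suppose 50 patients were held out and divided evenly over 5 strategies, leaving 10 per strategy. The standard error is √(p(1−p)/10): 14.5 points at 30% or 70%, and 15.8 points at 50%. That is too imprecise to validate individual strategies, so a split is not a practical remedy.

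**4. Optimism in the strategy picked as best.** Assumed, because the document does not give them: 3 to 5 strategies, the group sizes below, each patient counted under one strategy, and the true rates shown. Binomial responses were drawn 200,000 times. In each draw the strategy with the highest observed rate was picked, and optimism is its observed rate minus its true rate, averaged over draws.

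| Groups | True rates | Optimism (points) |
|---|---|---|
| 3 × 33 | all equal, 30%, 50% or 70% | +6.7 to +7.3 |
| 4 × 25 | all equal, 30%, 50% or 70% | +9.2 to +10.2 |
| 5 × 20 | all equal, 30%, 50% or 70% | +11.5 to +12.9 |
| 40/25/15/12/8 | all equal, 30%, 50% or 70% | +13.6 to +15.2 |
| 5 × 20 | 40, 45, 50, 55, 60% | +10.3 |
| 5 × 20 | 30, 40, 50, 60, 70% | +6.4 |
| 5 × 20 | four at 30%, one at 70% | +0.7 |

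For example, with 5 × 20 and a true rate of 50% throughout, the picked strategy shows 62.9% on average. In the last three rows the truly best strategy is picked in 48%, 70% and 98.5% of draws.

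**5. Whether the strategies are comparable at all.** In section 3, step 1 responds to raised intracranial pressure. Step 2 responds to low brain oxygen with impaired pressure reactivity, and step 3 follows if step 2 does not restore oxygen. Step 4 concerns low brain glucose when LPR has not been corrected, and step 5 follows failure of everything before it. Patients who reach different steps differ in pathology and in what has already failed. A ranking of steps by success therefore mixes the effect of treatment with the reason for giving it.

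**The case against.** The strongest reply is that the protocol is not derived from these data. The steps and most of their triggers are fixed beforehand, section 8.3 records prior review with unit staff and at a consensus meeting, and the primary question is whether this algorithm brings LPR below 25. In that sense *validate* may mean no more than a prospective check of a pre-specified bedside procedure. Part of this stands. A reader might infer that the overall LPR response is itself inflated by selection, or that nothing at all can be learned about the algorithm. The documents support neither, since no selection enters that rate and the prospective check is real. The check is weak, however. There is no comparator, and the Study Flow Chart admits patients once LPR is above 25, so some fall would be expected through regression to the mean.

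A second reply is that the optimism figures model a tidier trial than this one. That also stands. One patient may pass through several steps, the groups are not defined, and the secondary aim could mean the best correction for each abnormality and not a single winner. The figures illustrate a tendency and do not predict this trial's bias.

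A third reply is that resampling or another internal correction may be specified in a statistical analysis plan that is not shown. This is right, so its absence from the protocol is not counted as a defect.

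**Conclusion.** The point holds in two limited parts.

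First, the primary aim claims a property that the design does not have. One cohort at one centre on one algorithm can estimate the LPR response to within 9 to 10 points if all 100 patients contribute, but it cannot support a claim of validation. This rests on the protocol text alone.

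Second, reporting the superior or optimal strategy from the same patients will tend to overstate its success. The size depends on assumptions outside the document: about 7 to 15 points if strategies are truly equal, 6 to 10 points for the two graded spreads examined, and under 1 point if one is clearly best. A reader might take one of these as the expected bias, or attach it to the primary outcome. Neither is supported, because the document fixes neither groups nor rates, and the bias belongs only to the ranking.

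For the ranking, confounding of strategy with pathology and step order is a further problem that neither an optimism correction nor a new sample would remove.

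**What to change.** - Restate the primary aim in section 4 and the Study Summary as establishing the pre-listed algorithm and estimating the proportion of patients reaching LPR below 25, with its confidence interval. Leave validation to a later independent cohort.
- Label the strategy ranking in objective 1 and the secondary aim as exploratory.
- For any strategy reported as best, give an optimism-corrected estimate with an interval, for example by a bootstrap that repeats the selection in each resample. State beside it that this does not remove confounding by pathology and sequence.

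The cost is a change of wording, a short extra analysis in R (the software already named) and a more modest claim. No extra patients, measurements or changes to care are needed. The overall LPR rate stays as it is; only the figure quoted for a leading strategy may become less favourable.

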4.1 Objectives

1. We wish to determine which of the provided therapies that was superior to others in improving the deranged brain metabolism.
2. We also wish to determine the inter-relationships between parameters detected using the microdialysis and other monitoring techniques, such as brain oxygen saturation and perfusion pressure in the damaged brain, and how microdialysis may complement these techniques.
3. How the protocol will alter cytokine, chemokine and markers of brain damage markers (S100B) in serum and microdialysate for patients suffering from different pathological states?
4. How will the functional outcome distribution be for patients suffering from different pathological states?

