Study Co-ordinator	[name] [name], MD, PhD. Mail: Division of Neurosurgery, [name] [contact] E-mail: [contact] [contact]
Sponsor	[name], R&D Manager Mail: Cambridge University Hospitals NHS Foundation Trust, [name] [contact] E-mail: [contact] [contact]
Joint-sponsor(s)/co-sponsor(s)	University of Cambridge, Cambridge, United Kingdom
Funder(s)	Swedish Society of Medicine
Key Protocol Contributors	N/A
Committees	N/A

Directed management in brain injury.

STUDY SUMMARY

Study Title	Multimodality Monitoring Directed Management of Patients Suffering from Traumatic Brain Injury
Internal ref. no. (or short title)	Directed management in brain injury
Study Design	Controlled trial without randomisation
Study Participants	Patients with traumatic brain injury and need for intracranial monitoring.
Planned Size of Sample (if applicable)	100
Follow up duration (if applicable)	6 months
Planned Study Period	5 years
Research Question/Aim(s)	
Primary aim:
 
Establish and validate a clinical protocol for microdialysis derived chemistry driven therapy in TBI and see if it improves lactate:pyruvate ratio (<25).
 
Secondary aims:
 
Determine the optimal strategies for correcting abnormalities in microdialysis derived parameters.
 
Determine the inflammatory, tissue and functional outcome for patients suffering from different defined pathological conditions

Directed management in brain injury.

FUNDING AND SUPPORT IN KIND

FUNDER(S) (Names and contact details of ALL organisations providing funding and/or support in kind for this study)	FINANCIAL AND NON FINANCIAL SUPPORT GIVEN
Swedish Society of Medicine	214.000 SEK (Swedish Krona ~ 20.000£)

Directed management in brain injury.

ROLE OF STUDY SPONSOR AND FUNDER

The study sponsor will guarantee that the study will be performed according to rules and regulations, and will assume overall responsibility for the initiation and management of the study.

The Funder will guarantee salary for [name]. The funder will have no role in study design, conduct, data analysis and interpretation, manuscript writing, and dissemination of results.

Neither sponsors nor funder will have control over the final decision regarding any of these aspects of the study.

Directed management in brain injury.

ROLES AND RESPONSIBILITIES OF STUDY MANAGEMENT COMMITTEES/GROUPS & INDIVIDUALS

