8. ETHICAL AND REGULATORY COMPLIANCE	
9. DISSEMINATION POLICY	
10. REFERENCES	
11. APPENDICES	

Directed management in brain injury.

STUDY FLOW CHART

If a patient presents with a L/P ratio >25 we will include the patient in the study. As the different monitoring thresholds are reached, it will trigger different treatment strategies in order to treat a specific pathological substrate.

Excess serum, CSF and microdialysis samples will be stored for analyses of inflammatory markers and tissue damage markers.

Follow-up at 6 months following trauma will be done through outpatient clinic.

Directed management in brain injury.

STUDY PROTOCOL

Multimodality Monitoring Directed Management of Patients Suffering from Traumatic Brain Injury

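### Objective 1 asks which therapy is superior, but a single non-randomised ladder that assigns steps by state, prior failure or discretion cannot show this

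*Protocol*

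**What the plan says.** Section 4.1, Objective 1, reads: "We wish to determine which of the provided therapies that was superior to others in improving the deranged brain metabolism". It serves the first secondary aim in section 4, which is to find the optimal strategies for correcting microdialysis abnormalities. The outcome in section 4.2 is LPR below 25, achieved by different treatment strategies.

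The Study Summary gives the design as "Controlled trial without randomisation". No control group is described anywhere in the protocol. The Study Flow Chart says "If a patient presents with a L/P ratio >25 we will include the patient in the study" and "As the different monitoring thresholds are reached, it will trigger different treatment strategies".

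Section 3 sets out the ladder and argues: "As all patients will follow the same protocol, we will minimize the risk of selection and researcher bias". Its steps are entered as follows:

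- **Step 1:** raised ICP.
- **Step 2:** low brain oxygen with a raised pressure reactivity index.
- **Step 3:** "If this still does not improve the brain oxygen pressure", that is, after step 2 has failed on brain oxygen.
- **Step 4:** "These steps do not adjust the LPR and if there is a decrease in glucose", that is, after failure on LPR and with low brain glucose.
- **Step 5:** "If all the above steps fail to improve the LPR, it could be due to mitochondrial failure"; the options here are left to the treating physician.

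Section 5 plans comparative statistics between patients with different pathological targets. Section 8.1 says that the treating clinician's opinion will be respected for each patient.

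**The concern.** A claim that one therapy is superior to another needs patients in the same condition, at the same point, who received different therapies for reasons unrelated to their prognosis. The ladder plans no such contrast. Therapy is tied to the state that triggers it and, from step 3 on, to earlier failure. Where a clinician departs from the ladder, clinical judgement decides which patient gets what.

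The same-protocol argument in section 3 does not help here. For Objective 1, one protocol for all is what removes the within-state contrast.

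Before-after change within a step is no substitute. It is uncontrolled, and because the ladder is entered at LPR above 25, some patients will fall below 25 with no treatment effect.

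The final report could therefore name a superior therapy when the difference comes from the state treated, from the step's place in the ladder, or from untreated drift in LPR.

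**Working it through.** **Inputs.** The protocol supplies the ladder, the LPR threshold of 25 and n = 100. It gives no response rates, prevalence of the triggering states or LPR variability, so there is no figure of its own to reproduce. All rates below are assumptions, and each bias can be zero.

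**(a) Indication.** Let each therapy add 20 points, with untreated normalisation of 50% in one state and 30% in another. Apparent response is 50 + 20 = 70% against 30 + 20 = 50%. The table gives the chance that a pooled two-proportion z-test at two-sided 5% declares a difference, by exact binomial enumeration on separate groups. With n = 100, 25 per group corresponds to independent states at 50% prevalence, and 50 per group to mutually exclusive states.

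| Apparent response | 25 per group | 50 | 100 | 500 |
|---|---|---|---|---|
| 70% v 50% | 33% | 55% | 83% | >99% |
| 60% v 50% (untreated 40% v 30%) | 13% | 18% | 31% | 89% |
| 50% v 50% (no bias) | 7% | 6% | 6% | 5% |

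A larger trial makes the false difference more certain.

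**(b) Prior non-response.** Let every therapy succeed 50% of the time on average, with patient responsiveness p ~ Beta(2,2) shared across steps and each triggering state present in 50% of patients. Then E[p] = 0.5, E[(1−p)²] = 0.3, E[p(1−p)] = 0.5 − 0.3 = 0.2 and E[p(1−p)²] = 0.1.

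- Step 3, if entered only by patients whose LPR failed at step 2: 0.2/0.5 = 40%.
- Step 2, if also given only after step 1 fails (where step 1 applied): (0.5×0.5 + 0.5×0.2)/(0.5 + 0.5×0.5) = 0.35/0.75 = 47%.
- Step 3 under both conditions: (0.5×0.2 + 0.5×0.1)/(0.5×0.5 + 0.5×0.3) = 0.15/0.40 = 37.5%.
- Step 4 is about 43% in all four scenarios (simulation of 2,000,000 patients each).

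| Step 2 entry | Step 3 entry | Apparent success, steps 1/2/3/4 |
|---|---|---|
| State alone | Oxygen failure unrelated to LPR | 50/50/50/43% |
| State alone | Oxygen failure same as LPR failure | 50/50/40/43% |
| After step 1 fails | Oxygen failure unrelated to LPR | 50/47/47/43% |
| After step 1 fails | Oxygen failure same as LPR failure | 50/47/37.5/43% |

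The therapies are identical throughout, so step 3 ranges from no bias to about 13 points. If responsiveness is not shared across steps, every entry is 50%.

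**(c) Regression to the mean, no treatment effect.** Take normal readings with within-patient correlation r and the threshold at the median.

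- Next reading below 25 after one above: 1/2 − arcsin(r)/π. For r = 0.5, 0.8, 0.9 this is 33%, 20%, 14%.
- Reading after that, among those still above: 1 − [1/8 + 3·arcsin(r)/(4π)] / [1/4 + arcsin(r)/(2π)], for equal correlation between all readings. This is 25%, 13%, 8%.
- With 25 lying 1 SD below the median, the two sets are 11/7/5% and 9/5/3%.

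An ineffective therapy used early can thus look better than an equally ineffective one used later. If LPR does not fluctuate, the effect is zero.

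**The case against.** The strongest reply has five parts.

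- **No test between steps is specified.** Section 5 names only a contrast between pathological targets, which also fits Objectives 3 and 4. That is fair, and (a) is an illustration, not a critique of a stated test. But the objective itself asks for superiority between therapies, and any analysis that answers it must compare them.
- **Some overlap may exist.** Step 5 offers alternatives at one point, steps 2 and 3 act on the same low-oxygen state, and half-hourly microdialysis (section 7.2) permits within-patient analysis. Such analyses are possible, but step 5 is chosen by discretion and step 3 follows failure of step 2, so they remain confounded.
- **LPR above 25 is not among the inclusion criteria in section 7.1.1.** This is correct, although the Study Flow Chart makes it a condition of inclusion and section 3 makes it the trigger for the ladder. Regression to the mean follows from the trigger, so the caveat should refer to that.
- **The sizes depend on the model.** This stands. With serial (AR(1)) correlation instead of equal correlation, the second set in (c) becomes 31/18/12%, which narrows the gap between early and late steps to about 2 to 3 points. In (b), 47 to 50% of step 4 entrants had no earlier step. If instead every patient passed strictly from step to step, Beta(2,2) would give 50/40/33/29% for steps 1 to 4.
- **This is one exploratory objective, and the remedy is wording.** True, but the wording decides what the trial may conclude.

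**Conclusion.** The concern holds. Objective 1 claims something the design cannot deliver, and this follows from the allocation rule in section 3 without any of the assumed numbers. Because the ladder plans no same-state contrast between steps, neither a larger sample nor a later analysis plan can supply one. Departures by clinicians might create some overlap, but it would be unplanned and confounded.

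The size is unknown. Under the assumptions shown, identical therapies can appear to differ by 20 points through indication and by up to about 13 points through prior non-response. Between 14% and 33% of patients can cross the threshold at the next reading without any treatment effect when 25 is the median. Each figure falls to zero under the benign case named for it.

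The point is limited to Objective 1 and the first secondary aim. The primary aim, the other secondary aim and Objectives 2 to 4 are not challenged here. It should be fixed before results are reported.

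**What to change.** 1. In section 4.1, replace the superiority wording of Objective 1 with a descriptive aim, for example: *describe the change in LPR, and the proportion reaching LPR below 25, after each step among patients who enter it, within the state that triggers it; no ranking or superiority claim is made across steps.* Reword the secondary aim on optimal strategies in section 4 and the Study Summary in the same way.
2. State beside it that these before-after changes are uncontrolled and, because the ladder is triggered at LPR above 25, open to regression to the mean.
3. State that if the section 5 contrast between pathological targets is applied to LPR response, it is not evidence of a difference between therapies.

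**Cost.** A wording change and two sentences of caveat, with no new patients, visits or data and no change to any treatment step. What is given up is the superiority claim.

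The descriptive results will also be imprecise. If steps 1 and 2 are entered on state alone at an assumed 50% prevalence, about 50, 50, 25 and 25 of 100 patients enter steps 1 to 4. The 95% half-width around a proportion of 50% is 1.96×√(0.25/n), which is ±14 points for n = 50 and ±20 points for n = 25.

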1 BACKGROUND

Traumatic brain injury (TBI) is a major cause of morbidity and mortality worldwide especially in population under 40 years of age and has a significant socioeconomic impact. TBI results from the head impacting with an object or from acceleration/deceleration forces that produce vigorous movement of the brain within the skull, with the resultant mechanical forces potentially damaging glia, neurones, axons and blood vessels. The nature of the initiating force, as well as its site, direction and magnitude, determine the type and the severity of the injury¹. Contact trauma usually results in focal injuries such as skull fractures, extradural or subdural haemorrhages and contusions. Unrestrained head movement which generates acceleration/deceleration forces usually results in diffuse axonal injury^{1,2}.

The major determinant of outcome from TBI is the severity of the primary injury, which is irreversible. However, all neurological damage does not occur at the moment of initial injury, but evolves over the ensuing hours and days. Primary injury invariably leads to the activation of cellular and molecular responses which mediate secondary injury. These include an increase in extracellular levels of glutamate leading to excitotoxicity, the onset of oxidative stress, inflammation, disruption to the blood-brain barrier (BBB) and cerebral oedema formation, all of which exacerbate injury and tissue damage³⁻¹¹. Ultimately, all this leads to brain swelling within the confines of a fixed intracranial compartment, leading to increased intracranial pressure (ICP) and compromising cerebral perfusion pressure (CPP). Current ICU protocols for the treatment of TBI focus on the treatment of secondary injury and ensuring optimal cerebral perfusion¹²⁻¹⁸.

Most specialized neurocritical care units now use multimodality monitoring which involves placing intraparenchymal probes/catheters to measure the ICP (thus enabling the calculation of cerebral perfusion pressure), brain tissue oxygen tension (PbO₂) and microdialysis, in order to minimize secondary injury. However, all current clinical protocols are ICP based, i.e. a certain ICP threshold triggers a step wise treatment approach. At present, although there is evidence base to suggest their usefulness and potential for early detection of secondary, information that microdialysis or PbO₂ monitors provide has not been implemented in clinical protocols yet.

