7.2 Sampling

All patients will have a full medical history taken and a clinical examination. The following are to be recorded:

- a) Weight and BMI
- b) Sex
- c) Age and date of birth
- d) Any significant past medical history
- e) Full blood count (including platelets and differential white cell count)
- f) Biochemical series (including urea, creatinine, uric acid, electrolytes, calcium, alkaline phosphatase, AST, CRP and serum glucose)
- g) Initial Glasgow Coma Scale score
- h) Focal neurological deficit
- h) CT diagnosis, Marshall and Rotterdam score
- i) Drug dosages of paralyzing and sedating agents
- j) Drug doses of vasoactive agents
- k) Fraction of inspired oxygen (FiO₂), partial pressure of oxygen in arterial bloods (PaO₂) partial pressure of carbon-dioxide in arterial blood (PaCO₂)

Study Assessments

Dynamic	Multi-modality monitoring (ICP, CPP, PbtO ₂), MAP, FiO ₂
Every 30 minutes	Microdialysis Parameters
Hourly	GCS, Clinical examination, PaO ₂ , PaCO ₂ , serum sodium, serum glucose
2xDaily	Serum and if possible CSF sampling.

Brain imaging will be performed when clinically indicated.

All monitored parameters will be extracted automatically and stored on hospital computers as part of conventional care. Microdialysis sampling, as part of the standard routine, will be done twice hourly where 20 µl will be extracted. If the patient has an extra-ventricular drain, it will be used to sample cerebrospinal fluid as part of standard routine in the department (200 µl per sample, if available). Blood samples will be drawn twice daily, and we will use discarded samples for analysis (200µlx2 per day).

Directed management in brain injury.

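### Objective 3 asks what the protocol does to cytokines, chemokines and S100B, but with every patient on the protocol the design can only describe marker courses by pathological state

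*Protocol*

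**What the plan says.** Objective 3 in section 4.1 begins "How the protocol will alter cytokine, chemokine and markers of brain damage markers (S100B", and goes on to name serum and microdialysate and to refer to patients in different pathological states.

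The elements of the design that bear on it are:

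- **Comparator.** The Study Summary labels the study "Controlled trial without randomisation", but no control group is described. Section 3 says "As all patients will follow the same protocol, we will minimize the risk of selection and researcher bias".
- **Start of treatment.** The Study Flow Chart says "If a patient presents with a L/P ratio >25 we will include the patient in the study". Section 3 uses the same threshold to start the ladder. Neither place fixes a time after injury.
- **Marker samples.** The assessment table in section 7.2 has, twice daily, "Serum and if possible CSF sampling", and the text adds "Blood samples will be drawn twice daily, and we will use discarded samples for analysis". Section 7.2.2 (Sampling technique) describes all fluids as convenience samples. None is tied to the trigger.
- **Recorded items.** The section 7.2 list does not name time of injury.
- **Analysis.** Section 5 states one comparison only, between patients with different pathological targets.
- **Natural course.** The Background says "all neurological damage does not occur at the moment of initial injury, but evolves over the ensuing hours and days", and names inflammation among the secondary responses.

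**The concern.** To say that a treatment algorithm alters a marker, one needs to know what the marker would have done without it. Here nobody goes without it. The markers in Objective 3 reflect inflammation and tissue damage, the processes that the Background says keep changing after injury, so they can be expected to move whether or not the ladder works. The comparison that is planned, between states, answers a different question: whether markers differ by state among patients who all had the protocol.

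That comparison is exposed to time as well. The ladder starts when LPR exceeds 25, which can happen early or late. If one state tends to appear later after injury than another, its samples come from a later part of the natural course, and a difference between states could be a difference in timing.

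At stake is what the trial may conclude about its marker data. The LPR outcome in section 4.2 is not affected by this point.

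**Working it through.** **Step 1: the question set against the design.** There is no figure in the plan to reproduce for this objective. The n = 100 in section 7.2.1 comes without inputs, and the point does not depend on it.

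| What an effect on markers requires | What the protocol provides |
|---|---|
| Patients without the protocol, or an external reference matched on time since injury | None; all patients follow it (section 3) |
| A contrast that isolates the protocol | A contrast between pathological targets (section 5) |
| Knowledge of where each sample lies on the natural course | Time of injury not listed (section 7.2); convenience samples (section 7.2.2, Sampling technique) |

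The first row decides the matter. A pre-trigger sample would give a change from baseline, but that change is still natural course plus any protocol effect, and the two cannot be separated without a comparator.

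**Step 2: could timing matter between states?** The documents give no marker half-life, spread or timing gap, so every input here is an assumption except the total of 100 patients. Take two states of 50 patients each, a standard deviation of 1 on the natural-log scale, no true difference between states, and a marker with half-life h sampled g hours later after injury in one state.

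- Shift due to timing: δ = ln 2 × g / h
- Standard error: 1 × √(2/50) = 0.20
- Chance of a significant result in the direction of the gap (two-sided 5% test): Φ(δ/0.20 − 1.96), against a nominal 0.025

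For g = 24 h and h = 72 h: δ = 0.693 × 24/72 = 0.231; 0.231/0.20 = 1.155; Φ(1.155 − 1.96) = 0.21.

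| Half-life h | g = 12 h | g = 24 h | g = 48 h |
|---|---|---|---|
| 24 h | 0.41 | 0.93 | 1.00 |
| 72 h | 0.08 | 0.21 | 0.64 |
| 168 h | 0.04 | 0.07 | 0.17 |

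With g = 0 the excess vanishes. A rising marker with the same log shift gives the same chances.

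**Step 3: what a before/after reading would face.** The protocol does not plan one; this only shows why Objective 3 should not invite one. Assume 100 patients, change over 24 h, zero protocol effect, and a standard deviation s of 0.7 to 1.5 for the within-patient log change. The natural fall is 1 − 2^(−24/h), and the chance of a significant change is Φ(δ√100/s − 1.96) + Φ(−δ√100/s − 1.96) with δ = ln 2 × 24/h.

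| Half-life h | Natural fall in 24 h | Chance of significance (s = 1.5 to 0.7) |
|---|---|---|
| 24 h | 50% | 0.996 to 1.00 |
| 72 h | 20.6% | 0.34 to 0.91 |
| 168 h | 9.4% | 0.10 to 0.29 |

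The nominal rate is 0.05. These figures follow from assuming a steady decline and no treatment effect. They show that such a test would not be interpretable, not what the trial's markers will do.

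**The case against.** A reader might infer that the trial will report the natural course as a protocol effect. The documents do not support that. No section plans a before/after marker test or promises such a claim. Objective 3 ends by referring to pathological states, the secondary aim in section 4 concerns inflammatory, tissue and functional outcome by pathological condition, and the section 5 analysis is by pathological target. Read together, the intent is largely descriptive, and the trouble lies in one causal verb. This stands, and it is why rewording is sufficient.

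A reader might also take the missing baseline to be the root of the problem. It is not; the missing comparator is. Choosing a baseline sample from a series is ordinary analysis-plan work. With monitoring already in place and blood drawn twice daily, a sample near the trigger will often exist. This stands too.

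It can be said that injury timing is available anyway: a full medical history is taken, and a visit 6 months after trauma needs the injury date. That is fair for the date. For markers sampled twice daily the hour matters, and it is not a listed item. The trigger time can probably be recovered from the automatically stored monitoring data; listing it only makes that certain.

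Finally, the model term for time may sit in an analysis plan that is not shown. That is so, and its absence from the protocol is not the complaint. The wording of the objective and the list of recorded items belong to the protocol, and an analysis plan cannot dependably adjust for an hour that nobody was asked to record.

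Nothing in the documents shows that states trigger at different times, so the between-state confounding is a possibility, not a demonstrated bias.

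**Conclusion.** The point holds in a limited form. As worded, Objective 3 cannot be answered: with every patient on the protocol and a comparison only between states, a protocol effect on markers is not identified. This follows from the text and rests on no numerical assumption.

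The between-state comparison may in addition be confounded by time since injury. Its size is unknown from the documents. On the assumed half-lives of 24 to 168 h and a 24 h gap between two states, the chance of a spurious difference in the direction of the gap runs from 0.93 down to 0.07 against 0.025, and there is no excess if states trigger at similar times. The documents support neither a prediction of misreporting nor a specific percentage of marker change due to natural history.

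This is a secondary objective on leftover samples, so the point is moderate in weight. It is still worth acting on, because it changes what may be concluded and costs little.

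**What to change.** 1. Reword Objective 3 to describe marker levels and trajectories by pathological state, in line with the secondary aim in section 4, and make no claim that the protocol altered them.
2. Add date and time of injury, and time of the LPR >25 trigger, to the list in section 7.2.
3. Include hours since injury in the model for the twice-daily marker values, and likewise for markers measured in microdialysate.
4. The sample nearest the trigger may serve as a baseline covariate where one exists and the consent in place covers it, since inclusion occurs at the trigger and the next of kin or consultee must give written assent. State that a baseline does not by itself identify a protocol effect.

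The cost is one or two data items, one added model term and a weaker, descriptive claim. No extra samples are needed and patient management does not change. If the sponsor wishes to keep a claim of effect, it would need a comparator matched on time since injury, which is a different and larger undertaking.
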